P_1 = the expected population proportion in the comparison group of districts (set = 0.5 – this is the worst-case scenario and will produced a sample size that is adequate irrespective of the actual proportion)

P_2 = the expected population proportion in the intervention group of districts (set = 0.6 – assume minimum effect size to be realized of 10 percentages points)

$$P = (P_1 - P_2) / 2$$

$(P_1 - P_2)$ = the magnitude of comparison-group differences (or change over time) to be detected with the specified level of precision and power (assumed to be +/- 10 percentage points)

deft = design effect to compensate for clustering at the district level (1.5 assumed).

The required sample size is thus $n \geq 635$ per experimental group; ≥ 761 after 20% allowance for lost-to-follow up

³ Source: Lwanga SK and Lemeshow S. Sample Size Determination in Health Studies: A Practical Manual. Geneva: World Health Organization.

Interpretation: we would need to recruit 761 FSW who self-test for HIV testing in the intervention districts and 761 FSW for HIV testing at health facilities in comparison districts to be able to detect a 10 percentage point difference in the rate of HIV testing at health facilities (intervention vs. comparison districts) to have 95% certainty that a difference of that magnitude would not have occurred by chance and 90% certainty of detecting a difference of this magnitude if such a difference existed.

In order to assess whether “assisted” or “unassisted” community HIV screening among FSW results in a larger increase in the rate of HIV testing at health facilities, we would need samples of size $n \geq 761$ each of FSW who received assisted and unassisted screening in intervention districts, a total of $n \geq 1,522$ FSW in intervention districts, plus $n \geq 761$ in comparison districts.

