- How likely is it that the client will get a HIV test at a health facility as a result of the community screening test, on a scale of 1-5
- Comments and suggestions.

3. Routine Recording

Because of limitations in the data recorded and reported by health facilities, the study will rely primarily upon data recorded by IU outreach staff. Modifications will be made to the data recording and reporting systems currently being used to facilitate collection of the data needed for the study in a manner that minimizes additional recording and reporting burden. The nature of the adjustments to be made will be different for "assisted" and "unassisted" community screening.

To capture the data needed for of this study, the following data need to be recorded:

No	Data Recorded	Intervention Group	Control Group
1	Number of FSW contacted via outreach that were at least 6 months since their last HIV test for whom testing at a health facility was recommended	Yes	Yes
2	Numbers of FSW offered for HIV test at health facility	Yes	Yes
3	Numbers agreeing and disagreeing to testing at a health facility	Yes	Yes
4	Of those agreeing to getting tested at a health facility, the numbers that actually went to a health facility and were tested for HIV	Yes	Yes
5	Number of FSW offered for OFT screening	Yes	No
6	Among FSW not agreeing to be tested at a health facility, the numbers that agreed to (1) assisted community HIV screening and (2) unassisted community HIV screening	Yes	No
7	Numbers that were actually screened, assisted and unassisted	Yes	No
8	The number of community screening tests that were reactive	Yes	No
9	Among FSW with reactive community screening tests, the numbers that were subsequently tested at a health facility	Yes	No
10	Number of FSW initiating ART	Yes	Yes

For **unassisted** approach, additional information will be gathered as indicated below:

1. Numbers of FSW who access the link online
2. Numbers of FSW who are deemed eligible
3. Numbers of FSW who fill in baseline survey and agree to participate
4. Numbers of FSW who agree to take HIV test at health facility
5. Numbers of FSW who request the kit being delivered vs picking-up at fixed location
6. Numbers of FSW who upload the test result
7. Numbers of reactive vs non-reactive test result
8. Numbers of FSW who complete the post-test survey

9. Among FSW with community screening tests, the numbers that were subsequently tested at a health facility (reactive OR non-reactive)
10. Number of FSW initiating ART

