4. Numbering System for Test Kit and Other Instruments

a) Recording Test Kit ID

Every test kit will have a unique ID number, which will later be referred to as the Kit ID number. The Kit ID Number is to be filled in on all instruments and forms that are to be linked to the test results (e.g., baseline survey, test results form, post-test survey, routine data record in each IU, etc.). This number needs to be identified at all times to make sure that each participant is only assigned to one test kit, matching the kit with the results, and to track the stock of the test kit remained. The format of this ID kit will be “01-001”, where the first 2 digits are to identify the number of the district in which participants take the test, and the last 3 digits are to identify which test kit the participant is using. This test kit ID will also be later used for each IU to track the distribution of the test kit. Every test kit being distributed, either in a fixed place or delivered through same-day delivery services, will be recorded and tracked by each IU. An MS Excel or MS Access form will be developed to record and track the Kit ID Number.

b) Recording temporary FSW ID

On the ground of confidentiality, participants' full name will not be revealed and used within this study. A new system to ensure the reliable yet confidential identification of study participants needs to be established. Every participant in the study will be assigned to a temporary FSW ID. The format will be **the first 4 letters of participants' names added by the date of birth (yy/mm/dd)**. For example, a participant named “INDRIYANTI” who was born on March 5th 1976, her temporary FSW ID will be “INDR760305”. For FSW whose name contains only 3 letters, the number zero will be added after the last letter. For example, an FSW whose name is “AYU” and was born on March 5th 1976, her temporary will be “AYU0760305”. This temporary FSW ID will be used to ensure that each participant is only assigned to one test kit, to track test results, and to be filled in the baseline and post-test survey.

c) Matching Test Kit ID and temporary FSW ID

To match the test kit ID and temporary FSW ID, an automatic system needs to be developed to detect it precisely. This way, we can be sure that each participant only gets to participate in this study once (from receiving the kit, performing the test, and reporting the result).

d) Paper Based Data Collection

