In the event that participants' data are collected by paper, a procedure to upload the data into the established online system will be developed. Each data manager in the IUs needs to conduct the procedure regularly. This is to ensure that all data are being captured thoroughly.

F. DATA ANALYSES

The data analyses to be undertaken will be directed to addressing the research questions laid out at the beginning of the protocol and statistical tests appropriate to each specific analysis will be performed to inform the interpretation of results. The specific steps in the data analysis will be as follows:

1. Compare the characteristics of FSWs who receive self-testing and blood testing.

2. Compare the characteristics of FSWs who receive assisted and unassisted self-testing.
3. Compare proportion of FSWs taking confirmatory test out of those who receive the test in the assisted and unassisted self-testing.
4. Compare the proportion of FSWs who receive HIV test out of those who got offered for the test (including self-testing) in the intervention group with proportion of FSWs who receive HIV test in the control group.
5. Compare the proportion of FSWs taking confirmatory test (including self-testing) out of those receive the test in intervention groups and control group.
6. Compare the proportion of HIV positive in the assisted, unassisted (intervention) and HIV positive in the control group.
7. Compare the proportion of ART initiation in the assisted, unassisted (intervention) and the control group.
8. Calculate the cascade of HIV testing and treatment.
9. Compare stigma scores and FSWs who went to a health facility for HIV testing between assisted, unassisted group.
10. Compare the HIV and STI risk behaviors between assisted and unassisted group.

G. CONTINGENCY STUDY DESIGN

Should the OraQuick® test kits not become available in sufficient time to conduct a full-scale cRCT, a smaller-scale study will instead be undertaken. The purpose of the smaller study is the same as the cRCT described above, and the same protocol described above will be implemented. But the comparison is achieved targets between before and after intervention – there will be no comparison districts. The study will be undertaken in three (3) districts. The three districts will be selected from different parts of Indonesia, and they are: Kota Bandung (west part of Indonesia), Kota Denpasar (central part of Indonesia), and Kota Makassar (center-east part of Indonesia).

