Annex 5. VCT Test Confirmation and Result Form

FOLLOW-UP PARTICIPANT WHO CHOOSE TO PERFORM HIV BLOOD TEST AT HEALTH FACILITY

1	If participant agreed to perform HIV blood test in health facility, did she really go for it? (Needed to be validated at health facility)	1. Yes	2. No
2	Test result	1. Reactive	2. Non-reactive

FINAL

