Annex 8. Post-test Survey Questionnaire

KIT Code		0	1	-	0	0	1
Participant Code (First 4 letters, year, month, day)							
Name of OW/PE							
1.	Please write your full name or initials						
2.	How was the clarity of the information about HIV test kit you received/obtained? (Select one answer)	1. Extremely unclear					
		2. Unclear					
		3. Fairly clear					
		4. Clear					
		5. Extremely clear					
3.	When you performed HIV self-testing, was there any person (peer) who assisted you?	1. Yes					
		2. No					
4.	How easy was performing an HIV test using the self-testing kit given? (Select one answer)	1. Extremely difficult					
		2. Difficult					
		3. Fairly difficult					
		4. Easy					
		5. Extremely easy					
5.	What was the reason that prevented you from testing using the test kit provided?	1. Extremely difficult					
		2. Difficult					
		3. Fairly difficult					
		4. Easy					
		5. Extremely easy					
6.	This question only applies for those who underwent the self-testing assisted by OW/PE. How would you rate the given support by OW/PE /contact people who accompanied/contacted you during HIV self-testing? (Select an answer)	1. Extremely unclear					
		2. Unclear					
		3. Fairly clear					
		4. Clear					
		5. Extremely clear					
7.	This question only applies if your test results are negative. How much do you want to take an HIV test regularly after taking this test?	1. Extremely not in favour					
		2. Less in favour					
		3. Fairly in favour					
		4. In favour					
		5. Very in favour					
8.	How was your experience in performing this HIV self-testing (saliva test)?	1. Extremely unpleasant					
		2. Unpleasant					
		3. Fairly pleasant					

		4. Pleasant
		5. Extremely pleasant
9.	How sure are you with the accuracy of this test	1. Very doubt
		2. Less sure
		3. Fairly sure
		4. Sure
		5. Very sure
10.	How was your test result?	1. Positive
		2. Negative
		3. Indeterminate
11.	How much do you want to confirm your test results to the healthcare facilities?	1. Extremely unlikely
		2. Fairly unlikely
		3. Fairly likely
		4. Likely
		5. Extremely likely
12.	How likely are you to recommend your peers to undergo the screening test that you just performed?	1. Extremely unpleasant
		2. Unpleasant
		3. Fairly pleasant
		4. Pleasant
		5. Extremely pleasant
13	How much do you trust the accuracy of the test result	1. Extremely unsure
		2. Fairly unsure
		3. Fairly sure
		4. Sure
		5. Extremely sure
14.	What was your test result?	1. Positive → P.13

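### E.3's routine counts alone give no like-for-like assisted numerator for F.3's comparison of assisted and unassisted screening

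*Combined protocol and SAP*

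**What the plan says.** E.3 (Routine Recording) sets out the counts that the study needs and states that "the study will rely primarily upon data recorded by IU outreach staff". Its table covers the whole intervention group. Row 7 gives the number screened, separately for assisted and unassisted. Row 8 gives the number of reactive screens, not split by method. Row 9 gives later facility tests: "Among FSW with reactive community screening tests, the numbers that were subsequently tested at a health facility". It is not split by method either.

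A second list applies to the unassisted approach only. Its item 7 counts reactive and non-reactive results. Its item 9 reads "Among FSW with community screening tests, the numbers that were subsequently tested at a health facility (reactive OR non-reactive". Assisted women have no matching item.

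F item 3 reads "Compare proportion of FSWs taking confirmatory test out of those who receive the test in the assisted and unassisted self-testing". It serves Objective 3. B.5 describes the question as which method "results in a larger increase in the rate of HIV testing at health facilities" and asks for 761 women per method.

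B.1 suggests a confirmatory test to non-reactive women, C.2(f) offers assisted non-reactive women a referral card, and C.5 item 6 pays for the visit under both methods. B.1 also groups indeterminate results with reactive ones, and Annex 7 offers that category. C.2(e)-(f), C.3(f)-(g), C.5 items 5-6 and E.3 name only reactive and non-reactive.

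**The concern.** F.3 sets two proportions side by side. Its denominators are available by method from row 7. Its numerators, if taken from E.3, are defined differently: any result for unassisted women, and reactive results only for assisted women. Objective 3 concerns testing at health facilities in general, so a visit after a non-reactive screen belongs in the outcome. The plan invites and pays for such visits, but E.3 does not list them for assisted women.

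At stake is whether a comparison attached to a primary objective can be built from the study's stated main data source. The indeterminate category is a smaller matter of consistency: B.1 sets a rule that the outreach steps, payment list and counts do not repeat.

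**Working it through.** The plan gives no figure on this point, so there is none to reproduce. The check has two parts.

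**1. What E.3 can supply to F.3**

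| F.3 needs | Assisted | Unassisted |
|---|---|---|
| Women screened | Row 7 | Row 7 |
| Facility tests after a reactive screen | Row 9, pooled over methods | Row 9, pooled; or item 9, if kept by result |
| Facility tests after a non-reactive screen | No item | Item 9 |
| Facility tests after an indeterminate screen | No item | Not named |

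Row 4 does not fill the gap. It covers women who agreed to facility testing at the first offer, whereas women reach screening by declining that offer.

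Subtraction does not give a full assisted numerator either. Row 9 minus the unassisted reactive visits would leave assisted reactive visits, but item 9 is not stated to be kept by result. Even with that split, assisted non-reactive visits would still be missing.

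The visible forms do not close the gap:
- Annex 5 asks "If participant agreed to perform HIV blood test in health facility, did she really go for it", so it concerns women who agreed to the blood test.
- Annex 7 holds kit code, participant code, method and screen result, but has no attendance field.
- Annex 8 item 11 asks "How much do you want to confirm your test results to the healthcare facilities", which is intention, not attendance.

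**2. Ceiling on a reactive-only assisted numerator**

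Inputs:
- Positivity 3%: B.5 assumes this for facility testing. Applying it to screened women is an assumption, so a range of 1% to 10% is shown.
- Sensitivity 90.14% and specificity 99.13%: the evaluation quoted in A.3.
- 761 assisted women: B.5.

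Reactive share R = positivity × sensitivity + (1 − positivity) × (1 − specificity), with indeterminate results ignored.

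- 3%: R = 0.03 × 0.9014 + 0.97 × 0.0087 = 0.0270 + 0.0084 = 0.0355; 761 × 0.0355 ≈ 27 women.
- 1%: R = 0.01 × 0.9014 + 0.99 × 0.0087 = 0.0176; about 13 women.
- 10%: R = 0.10 × 0.9014 + 0.90 × 0.0087 = 0.0980; about 75 women.

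Even if every reactive woman attended, a reactive-only assisted proportion could not exceed about 3.5% of those screened (1.8% to 9.8% over the range). The unassisted proportion, defined by item 9, could in principle reach 100%. The two are not comparable.

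**The case against.** The strongest reply is that E.3 lists summary counts, while the plan implies attendance data on each woman.

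- E.1 intends to predict from stigma items who presented for formal testing, and F item 9 compares stigma and facility attendance between the two methods. Both need attendance for each woman, not limited to reactive screens.
- C.2(g), in the assisted section, keeps the current tracking of who was tested. C.2(a) says the referral card helps to count those tested, and C.2(f) offers the card to non-reactive women. The card in Annex 9 carries the kit code.
- E.4(a) says: "The Kit ID Number is to be filled in on all instruments and forms that are to be linked to the test results".
- C.5 items 5 and 6 pay for confirmatory visits by screen result under both methods, which requires knowing who attended. C.5 also pays facilities to collect confirmatory-test data for both methods.
- E.3 says that recording will differ by method.
- Annex 1, the flowchart of routine recording, is not visible in the text reviewed, so nothing can be concluded from it.

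Most of this stands. Several of these are outreach records, so E.3's reliance on outreach staff does not rule them out. They show that the missing visits may be recoverable. They do not state that these records will supply F.3's numerator, and different collection routes do not justify different outcome definitions for two groups that are compared directly.

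A reader might go further and infer that unassisted screening will look better. If row 9 were split by method and used as worded, the false gap would be (1 − 0.0355) × q = 0.9645q, where q is the share of non-reactive women who attend, equal in both methods: 4.8 points at q = 5%, 9.6 at q = 10%. The documents do not support this as a finding. They do not give q, F.3 does not say row 9 will be used this way, and the figure assumes no recovery from other records and complete capture of unassisted visits, although those women may be harder to follow. With full recovery on the assisted side the gap is zero. Nor do the documents show that the visits would be lost for good.

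**Conclusion.** The point holds in a limited form. As written, E.3 gives F.3 no assisted numerator comparable with the unassisted one, although F.3 addresses a primary objective. The supportable measure of size is the ceiling of about 3.5% of assisted screens, against no such ceiling for unassisted screens. It rests on 3% positivity among screened women, the quoted test performance and no indeterminate results. The mismatch of definitions needs none of these assumptions.

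The size and direction of any bias in the final comparison are not established, because other planned records may supply the missing visits. The omission of indeterminate results is minor, since B.1 already sets the rule and Annexes 7 and 8 record the category. A reader might also object that C.2(f) and C.3(g) encourage testing less than B.1 does. That is a matter of wording which applies alike to both methods, and B.1 itself intends lighter encouragement after a non-reactive screen.

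**What to change.** 1. Reword E.3 rows 8-9 and unassisted items 7 and 9 to count screen results (reactive, non-reactive, indeterminate) and later facility tests after each, separately for assisted and unassisted women.
2. Extend the Annex 5 attendance follow-up form, with kit code, to all screened women, using the attendance already tracked through referral cards and incentive payments. Annex 7 is the wrong place, because it records the screen result and attendance comes later.
3. Define F.3's numerator as facility tests after any screen result, and also show it by result.
4. As a minor consistency edit, name indeterminate results alongside reactive ones in C.2(e), C.3(f) and C.5 item 5, to match B.1.

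The cost is slightly more recording work for outreach staff, since most screened women will be non-reactive and their attendance must also be entered. No extra participants or study visits are needed.

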The study will produce scientifically strong evidence as to whether two alternative models of community HIV screening among FSW (assisted and unassisted) result in (1) increased rates of formal HIV testing at health facilities and (2) increased rates of treatment initiation in districts in which the community screening intervention is added to the existing FSW community outreach model.

Two alternative study protocols are described in this document. The bulk of this document presents a protocol for a community randomized controlled trial (cRCT), which is the preferred research design option. However, due to a delay in procurement of the OraQuick® rapid HIV test kits that are to be used in the study, there may be insufficient time to undertake a full cRCT.¹ Accordingly, a contingency protocol that can be implemented in a shorter period of time is also presented.

6. Study Objectives

The primary objectives of this study will provide answers to the following five (5) questions:

1. Does the proportion of FSW who know their HIV status increased?

¹ All research activities must be completed by 31 December 2020.

2. Does the introduction of community HIV screening among FSW increase the rate of HIV testing at health facilities?
3. Does “assisted” or “unassisted” community HIV screening among FSW result in a larger increase in the rate of HIV testing at health facilities?
4. Does “assisted” and “unassisted” community HIV screening among FSW results in a larger increase in the rate of HIV positive case finding?
5. Does the introduction of community HIV screening among FSW increase the rate of initiation of ART?

The secondary objectives of this study will provide answers to the following two (2) questions:

1. What is the acceptability of community-based self-screening for FSWs participating in this study?
2. What is the satisfaction of FSWs participating in this study towards delivery of community-based self-screening?

B. STUDY DESIGN

1. Design Summary

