The flowchart of the study is presented in Figure 1. Randomization was carried out among the 23 priority districts in this study with a ratio of 2:1 (that is, 2 intervention districts per 1 control district). The details of randomization are explained in section B.4 of this document. **The assigned 15 intervention districts and 8 comparison districts** are described in Table 6. Potential participants in the intervention area will be screened through the inclusion and exclusion criteria established for

this study. The criteria for participants who are eligible for this study are explained in section B.3 of this document and Annex2.

According to the Indonesian Ministry of Health's current recommendation, HIV blood test at an authorized health facility is still the current practice for HIV diagnosis. Both participants in the intervention and comparison area will be offered for HIV blood test at a health facility. Participants in comparison areas and participants in intervention areas who agree to take HIV test at a health facility will then be managed further according to the existing guideline or "standard of care." For participants in intervention areas who refuses to have her blood drawn for HIV test at a health facility will then be offered self-testing using OraQuick®. Participants will then fill and sign the informed consent to participate in CBS study.

Next, participants will be offered to do the test assisted or unassisted. If the participant chooses to perform the test assisted, the PL/PE will help her from filling in a baseline survey, performing the test, and filling in a post-test survey. If the participant chooses to perform the test unassisted, there will be two options for the participant to get the test kit. First, PL/PE will deliver the test kit for the participant, help with filling in the baseline survey on the spot and give information about uploading test results and the post-test survey, along with a hotline number to call for any questions and concerns, including follow-up steps after participants have received the results. The second method, participants will be given a link online which will entitle information of this study, eligibility criteria, informed consent, baseline survey, link to order a test kit, link to upload result and link to fill in the post-test survey. Participant who chooses this second method will also be given hotline number should there be any further inquiries.

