
3. Implementation Guidelines: Unassisted Community Screening

Because of differences in the structure of sex work and in the enabling environment in different districts, it will be necessary to develop the details of unassisted community screening on a district-by-district basis. Ideally, the same unassisted community screening intervention would be implemented in the same way in all intervention districts, but if this is not possible due to the factors outlined above, allowing some details to vary across districts is preferable to trying to implement a standard protocol that is expected a priori to fail in some locations.

For unassisted community screening, in which OW don't have face-to-face contact with FSWs, possible mechanisms for distributing Ora-Quick test kits entail:

- a. Trained PE/PL identifying various online networks in which FSWs use to solicit their service.
- b. Trained PE/PL building trust from FSWs to participate in the study.
- c. Trained PE/PL send broadcast message containing brief information of the study, eligibility criteria for participation, step-by-step method to order the kit and have it delivered to their address, short link for description of how to use the kit (flier or short video), and mandatory baseline and post-test survey. Test kit delivery will be done by same-day delivery system (Go-Send/Grab Send) from selected places where the test kit will be stored (Implementing Unit Office or selected health care facilities) to client's address. Trained peer leader/peer educator could also distribute the test kit but not participating in the testing by assisting FSW during the test.

- d. Trained PE/PL carrying out follow-up for FSWs being previously approached for the test. The same trained PE/PL is assigned to be the contact person/hotline for each FSW they approached and agreed to take the test.
- e. FSW send/upload results of the test along with a completed post-test survey. Cash (mobile top-up) incentive will be transferred to FSW who send the test results and post-test survey. Every kit distributed will have unique code and FSW will be asked to fill it in both baseline and post-test survey to ensure one FSW is entitled to only one test kit.

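### Assisted and unassisted screening share the same 15 districts, but their comparison has no district term and borrows a between-district sample size

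*Combined protocol and SAP*

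**What the plan says.** Objective 3, one of the primary questions in A.6, asks which of the two screening methods will "result in a larger increase in the rate of HIV testing at health facilities". The trial has "The assigned 15 intervention districts and 8 comparison districts" (B.1). Method is not allocated at either level. A woman in an intervention district who declines a facility blood test chooses for herself: "Next, participants will be offered to do the test assisted or unassisted" (B.1; C.1 says the same). Both methods are therefore offered inside each intervention district.

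B.5 defines its multiplier as "deft = design effect to compensate for clustering at the district level (1.5 assumed") and arrives at 635 per group, 761 after the 20% allowance. For Objective 3 it reuses that figure: "we would need samples of size $n \geq 761$ each of FSW who received assisted and unassisted screening in intervention districts", 1,522 in all.

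C.3 says of the unassisted method that "it will be necessary to develop the details of unassisted community screening on a district-by-district basis", while noting that uniform delivery would be ideal.

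F item 3 is to "Compare proportion of FSWs taking confirmatory test out of those who receive the test in the assisted and unassisted self-testing". It gives no stratum, model or district term. The introduction to Section F promises only suitable tests for each analysis. Multivariable analysis appears only in B.5, for the impact estimate from SIHA data. Section G repeats item 3 for three districts. E.4(a) says of the kit code that "the first 2 digits are to identify the number of the district in which participants take the test".

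**The concern.** District is a matching factor for this contrast, and neither the sizing nor the analysis treats it as one. If facility testing differs between districts and so does the method mix, the method used mainly in high-testing districts looks better without being better.

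An illustration uses B.5's own proportions as the rates of two equal-sized districts, 0.5 and 0.6, identical for both methods within each. Let the assisted share be 20% in the first and 80% in the second. The pooled assisted proportion is 0.2 x 0.5 + 0.8 x 0.6 = 0.58. The pooled unassisted proportion is 0.8 x 0.5 + 0.2 x 0.6 = 0.52. That is a 6-point gap with no method effect anywhere.

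This arises even if choice within a district is random, so adjusting for women's characteristics does not remove it. At stake is which delivery model the trial appears to favour.

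**Working it through.** **1. The plan's own size.** Inputs from B.5: P1 = 0.5, P2 = 0.6, Z = 1.282 for power, multiplier 1.5, allowance x 1.2; P is read as the mean, 0.55. The formula is n = [Zα√(2P(1-P)) + Zβ√(P1(1-P1) + P2(1-P2))]² / (P1-P2)².
- With Zα = 1.645: n = 423; x 1.5 = 634.5, i.e. 635; x 1.2 = 761. This reproduces the plan.
- With the stated Zα = 1.96: 519; x 1.5 = 779; x 1.2 = 934. This mismatch is a separate matter, but it means that B.5's power cannot be compared directly with that of a stratified test.

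**2. The ICC implied by the 1.5.** From 1.5 = 1 + (m-1) x ICC:
- m = 1,522/15 = 101.5 women per district gives ICC = 0.5/100.5 = 0.005.
- m = 761/15 = 50.7 per method per district gives 0.5/49.7 = 0.010.

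**3. False-positive rate of an unadjusted pooled test.** Let a_j and u_j be district j's shares of the assisted and unassisted totals. The true variance relative to the assumed variance is

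R = (1-ICC) + ICC x Σ(a_j-u_j)² / (1/N_A + 1/N_U).

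With equal districts and an overall even split, the last factor is 101.5 x 4 x SD², where SD is the standard deviation of the assisted share across districts. The rejection rate is 2[1-Φ(1.96/√R)]. Example: ICC 0.01, SD 0.3 gives R = 0.99 + 0.01 x 101.5 x 0.36 = 1.355 and a rate of about 9%.

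Rates averaged over random mixes (ICC and SD are assumptions):

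| ICC | SD 0 | SD 0.1 | SD 0.2 | SD 0.3 | SD 0.4 |
|---|---|---|---|---|---|
| 0.005 | 4.9% | 5.2% | 5.8% | 7.0% | 8.7% |
| 0.01 | 4.9% | 5.3% | 6.7% | 9.1% | 12.4% |
| 0.02 | 4.8% | 5.6% | 8.4% | 13.0% | 19.0% |
| 0.05 | 4.4% | 6.6% | 13.3% | 23.2% | 33.1% |

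For scale, a share uniform on 20-80% has SD 0.17, and on 5-95% SD 0.26. District sizes proportional to Table 5 raise the figures somewhat (ICC 0.01, SD 0.3: 10%). Simulation (4,000 runs per cell) agrees with the table. A Cochran-Mantel-Haenszel test stratified by district rejected 4.4-5.4% throughout, with no peer-worker clustering in the model.

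**4. What doubling requires.** A 10% rate needs R = (1.96/1.645)² = 1.42. The share SD must then be at least 0.46, 0.33, 0.23 or 0.15 at ICC 0.005, 0.01, 0.02 or 0.05.

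**5. A rough ICC from the plan's tables.** Twice Table 4 over Table 5 runs from 0.17 (Deli Serdang) to 0.68 (Sorong) across the 15 districts: mean 0.382, SD 0.145, ICC = 0.145²/(0.382 x 0.618) = 0.089. With one semester it is 0.034. Weighted by Table 5 the two become 0.056 and 0.022.

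**6. Whether the 1.5 suits this contrast.** If it were also applied in the pooled test, simulated rejection would be 1.2-1.6% with an even mix, 4.1% at ICC 0.01 and SD 0.3, and 14.2% at ICC 0.05 and SD 0.3. It is too large in one setting and too small in another.

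**7. Power.** The stratified test at 609 analysed per method (761 less 20%) and a 20-80% share has about 91% power for 10 points if women within a district are independent. One peer worker assists many women, however. With an assumed worker-level ICC of 0.05 and unclustered errors, that test rejects a true null 5.9%, 7.2% and 11.4% of the time at 5, 10 and 20 assisted women per worker. The last two imply variance inflation of about 1.19 and 1.54. Since 91% power corresponds to 1.96 + 1.34 = 3.30 standard errors:
- 10 per worker: 3.30/√1.19 - 1.96 = 1.07, power about 86%.
- 20 per worker: 3.30/√1.54 - 1.96 = 0.70, power about 76%.

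**The case against.** Section F names no test, so a pooled analysis is an inference from silence, and a careful analyst might stratify anyway. That is correct, but for a primary question the silence leaves the choice open until the data have been seen.

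A reader might infer that false positives more than double. The documents do not support that. They give neither the ICC nor the mix, an even mix produces no inflation, and at the ICC implied by the 1.5 doubling needs a share SD of about 0.33 or more. The higher ICCs from Tables 4 and 5 are only a proxy. They divide programme tests by outreach contacts, whereas item 3 concerns confirmatory testing among women who had declined a facility test and then self-screened.

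A reader might also infer that B.5 ignores clustering. It does not: the 1.5 is there, and with an even mix it more than covers a within-district contrast. The criticism is only that it was set for a different one.

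C.3 shows that delivery may vary locally, not that the mix will, so uneven shares are plausible rather than established.

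Finally, stratifying leaves the larger threat in place, because women choose their method. That stands in full. District adjustment removes one source of confounding and does not make the comparison causal.

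**Conclusion.** The point holds as a conditional one. The plan compares two methods offered in the same 15 districts without a district term, and sizes that contrast with a figure built for a comparison between districts. If the mix varies (share SD 0.1-0.3), a pooled two-sided 5% test rejects a true null about 5-9% of the time at ICC 0.005-0.01 and about 6-23% at ICC 0.02-0.05. More extreme mixes or higher ICCs give more; a uniform mix gives no excess. These figures rest on assumed ICCs and mixes, roughly equal overall numbers per method and, for the main table, equal district sizes.

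A single power figure of 91% for the stratified test should not enter the plan, since plausible peer-worker clustering could bring it to about 76%.

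**What to change.** - **F item 3:** state that assisted and unassisted are compared within district, by a Mantel-Haenszel risk difference or a logistic regression with district fixed effects, taking district from the first two digits of the kit code. Use standard errors clustered by peer worker; the survey forms have a field for the worker's name. Report the assisted share and both proportions by district.
- **Other assisted-unassisted comparisons** (items 2, 9 and 10, the assisted-unassisted part of items 6 and 7, and the same items in Section G): apply the same district adjustment. In Section G there would be three strata.
- **B.5:** keep 761 per method as the recruitment target, but say that the 1.5 was not derived for this within-district contrast. Give power as a range over method mix and peer-worker clustering.
- **Interpretation:** state that the comparison is observational because women choose the method.

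The cost is a few sentences, with no new participants and no new district data. Some power is lost if the mix is very uneven: with 1,522 women and ICC 0.01, simulated stratified power is about 97%, 95% and 87% at share SD 0, 0.2 and 0.3, before losses and worker clustering. Districts using only one method contribute nothing to the estimate, and intervals widen with clustering by worker.
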